9.4.4 SAFETY ANALYSES

All treatment emergent adverse events will be tabulated and summarized between the study groups and presented in a series of tables using standard Medical Dictionary for Regulatory Activities (MedDRA) terminology.

9.4.5 BASELINE DESCRIPTIVE STATISTICS

We will use descriptive statistics to describe the data for each of the study groups. Categorical variables will be presented as proportions and means with standard deviation and range. We will assess the groups in terms of baseline demographics, comorbidities, prior medications, and disease comparisons.

9.4.6 PLANNED INTERIM ANALYSES

There are no planned interim analyses for this study. The Data and Safety Monitoring Board (DSMB) will review all SAEs as soon as they are reported, and all AEs at the pre-set meeting intervals. If two grade 3 related or possibly related events occur, the DSMB will review all AE data at that time. If there is an unexpected signal or safety concern or newly identified risk that would potentially outweigh the potential benefits of the study drug, then temporary suspension of the study could be considered. See section 10.1.2 for additional details.

9.4.7 SUB-GROUP ANALYSES

In accordance with the first additional aim (“to determine predictors of symptomatic and histologic response to mepolizumab treatment, including potential biomarkers”), we will perform prespecified planned analyses of the primary or secondary outcomes by age, sex, and race/ethnicity, depending on the final characteristics of the population enrolled in the study.

9.4.8 TABULATION OF INDIVIDUAL PARTICIPANT DATA

Data will be analyzed in the aggregate, so we are not planning any primary analyses which present individual data by measure or time point. Depending on the results and data distributions, however, this may be done in exploratory fashion.

9.4.9 EXPLORATORY ANALYSES

Prespecified exploratory outcomes are as follows:

- Mean change in peripheral blood eosinophil levels from baseline to 3-months post-treatment. This will be compared between the groups using analysis of covariance.
- For patients initially randomized to active medication, the same set of outcomes (as listed above) will be assessed after 6 months of treatment. This will be compared between the groups using analysis of covariance.
- For patients initially randomized to placebo, a paired analysis will be conducted to compare month 3 to month 6 outcomes. This will use paired t-tests for continuous variables and McNemar's test for categorical variables.
- For the same set of outcomes (as listed above), 3-month data for patients initially randomized to active medication (300mg monthly) will be compared to 6 month data for patients initially randomized to placebo and who have completed 3-months of 100mg monthly. This will provide a comparison of the 300mg to the 100mg dose.
- Adverse events and safety during all time points in the study. This will be compared between groups by chi-square.

Additional Exploratory outcomes are as follows:

- Change in weekly SDI score over the course of the study, and correlation of SDI with the EEsAI score. We will also explore the minimal clinically important differences (MCIDs) of these measures.
- Biomarkers, including serum and tissue levels of cytokines and related factors (IL-5, IL-13, and eotaxin-3 [CCL26]), and eosinophil granule levels (i.e. eosinophil peroxidase or major basic protein) in blood and tissue.
- Antibodies to mepolizumab as a measure of immunogenicity. The study sponsor will assist with these measurements.
- Additional histologic findings, including eosinophil degranulation, microabscesses, basal layer hyperplasia, spongiosis, and lamina propria fibrosis (in samples with adequate subepithelial tissue present).
- Response outcomes (noted above) in prior steroid responders vs. non-responders. Steroid non-response is defined as greater than 15 eos/hpf after a 2-month course of a swallowed/topical steroid at a standard dose (standard dose = 2mg/d of budesonide or 1760 mcg/d of fluticasone). Of note, the randomization is balanced for prior steroid response, but the study is not powered for this exploratory outcome. We will also explore the response outcomes in the context of all prior EoE treatments to understand heterogeneity of treatment response, if present, and will include this stratification factor as a covariate in the above analyses, as appropriate.
- Response outcomes (as noted above) in patients on a restrictive diet vs. an inclusive diet. A restrictive diet will be defined as any diet at baseline (which also must be maintained through the study) that is either limited in foods because of EoE or because of food allergies/intolerances.

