1 PROTOCOL SUMMARY

1.1 SYNOPSIS

Title: A multi-center, randomized, double blind, parallel-arm, placebo controlled trial of mepolizumab for treatment of adults and adolescents with active eosinophilic esophagitis and dysphagia-predominant symptoms

Study Description: This multi-center, randomized, double blind, parallel-arm, placebo controlled trial will determine whether mepolizumab is more effective than placebo for improving symptoms of dysphagia and decreasing esophageal eosinophil counts in adults and adolescents with active eosinophilic esophagitis after an initial 3-month treatment course and will also assess the impact of an additional 3-months of treatment.

Objectives: Primary Objectives:

1. To determine whether mepolizumab is more effective than placebo for improving symptoms of dysphagia as measured by the validated Eosinophilic Esophagitis Symptom Activity Index (EEsAI) in adults and adolescents with active eosinophilic esophagitis after a 3-month treatment course.
2. To determine whether mepolizumab is more effective than placebo for decreasing esophageal eosinophil counts in adults and adolescents with active eosinophilic esophagitis after a 3-month treatment course.

Secondary Objectives:

1. To determine predictors of symptomatic and histologic response to mepolizumab treatment, including potential biomarkers.
2. To assess durability of symptomatic and histologic response to mepolizumab after 6 months of treatment in patients initially randomized to the active medication (this includes a 3-month blinded second phase of treatment).
3. To assess histologic response to a lower dose of mepolizumab treatment in patients initially randomized to the placebo arm (this will be in a 3-month blinded second phase); symptom response will also be assessed in this phase.
4. To assess safety of mepolizumab over 3 and 6 months of treatment (this includes both 3-month study phases).

Outcomes:

Primary Outcome:

1. Mean change in dysphagia as measured by the EEsAI score (7-day recall) from baseline to 3-months post-treatment.

Secondary Outcomes:

1. Proportion of patients who have clinical remission as defined by an EEsAI score of ≤ 20 .
2. Proportion of patients who have a clinical response, as defined by an EEsAI score decrease of ≥ 20 points.
3. Absolute peak eosinophil count (measured in eos/hpf) after 3-months of treatment.
4. Levels of histologic response after 3-months of treatment including < 15 , ≤ 6 , and ≤ 1 eos/hpf.

[figure not shown]

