6.5.1 PROHIBITED TREATMENTS

No dietary changes, dilations, changes in baseline PPI medication dose, changes in inhaled or intranasal steroid doses, or administration or oral, topical/swallowed, or systemic steroids will be allowed during the study period (from consent through the end of treatment period). Esophageal dilation at the screening or month 3 endoscopy will result in study exit. However, dilation may be performed during or after the month 6 endoscopy, if clinically indicated.

If a subject has severe persistent or recurrent symptoms, or experiences a food impaction during the treatment period, rescue medications and procedures to treat EoE are allowed for clinical purposes. The sponsor will not supply rescue medications, and these would need to be prescribed as clinically indicated by the subject's physician. However, if such medications or treatments are required, the participant would be considered a treatment failure and would exit the study. If this happens, and at the discretion of the site-Investigator or sponsor-investigator it is safe and feasible to do so, the subject should return for an early termination visit.

Although the use of rescue medications is allowable at any time during the study, if safe and feasible to do so the use of rescue medications should be delayed until either the 3-month or 6-month assessments are completed. Rescue medications or treatments administered after the month 6 EGD will not result in study exit. The date and time of rescue medication administration as well as the name and dosage regimen of the rescue medication must be recorded.

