9.4 STATISTICAL ANALYSES

9.4.1 GENERAL APPROACH

Descriptive statistics will be used to describe the data. Categorical variables will be presented as proportions and means will be presented with standard deviation and range. If the data are not normally distributed, medians and interquartile ranges will be presented rather than means, and non-parametric testing will be used. For inferential tests, a p value < 0.05 will be considered significant and all tests will be two tailed. All statistical estimates (e.g., medians, proportions, incidence rates, mean differences, correlations, etc.) will be tabulated along with corresponding confidence intervals (CIs).

Interpretation of CIs will play a major role as an integral part of the analysis of the data in concert with any statistical hypothesis tests. To avoid over-reliance on p-values, the magnitudes of estimates and the corresponding confidence intervals will be a focus of the analyses. Reasons for missing data will be investigated and recorded for purposes of statistical analyses. Because of the study design and outcome assessment, primary analyses will require exclusion of participants without outcome data. However, we will perform sensitivity analyses for missing data, initially assigning participants lost to follow up to treatment failure, then assigning them to treatment success and comparing the results, a technique that has been successful in prior clinical trials conducted by our group. For all outcomes, the null hypothesis is that there is no difference between the study groups. All hypothesis tests that are observed to be NOT statistically significant will be reported as being inconclusive.

The study statistician on this study will be [name].

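### The month-6 durability analysis has no analysis set and no rule for rescue exits, so excluding those exits would overstate durability

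*Combined protocol and SAP*

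**What the plan says.** Secondary Objective 2 in the Synopsis is: "To assess durability of symptomatic and histologic response to mepolizumab after 6 months of treatment in patients initially randomized to the active medication". The matching analysis is listed among the prespecified exploratory outcomes in Section 9.4.9: "For patients initially randomized to active medication, the same set of outcomes (as listed above) will be assessed after 6 months of treatment". That bullet goes on to mention a between-group analysis of covariance, but gives no month-6 population and no handling of exits.

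Section 6.5.1 says of rescue during the treatment period: "However, if such medications or treatments are required, the participant would be considered a treatment failure and would exit the study". It also says: "Esophageal dilation at the screening or month 3 endoscopy will result in study exit". Rescue after the month-6 endoscopy does not cause exit.

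On missing outcomes, Section 9.4.1 says that "primary analyses will require exclusion of participants without outcome data". It adds a sensitivity analysis that counts participants lost to follow-up first as failures and then as successes. Section 9.3 defines the modified intention-to-treat set on 3-month data, and plans a sensitivity analysis that carries the last EEsAI forward for participants who terminate or are lost to follow-up.

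**The concern.** Durability asks whether a response lasts. A patient who relapses badly enough to need rescue between months 3 and 6 has answered that question, and the protocol already calls that patient a failure. The same event ends study participation, so the patient has no scheduled month-6 value. Nothing in Section 9.4.9 carries the failure label into the analysis.

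If the analyst falls back on the only default the plan states, these patients leave both numerator and denominator. The month-6 remission, response and histology rates then describe patients who did not need rescue. At stake is how the 6-month result for the 300 mg arm is read: the missing values arise partly from the outcome being measured, and the error runs toward durability.

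**Working it through.** **The plan's own figures.** No durability figure is stated, so there is none to reproduce. The arm size used below comes from Section 9.2. With a difference of 17, SD 20, two-sided alpha 0.05 and power 0.90, 30 per group is reproduced (power 0.909 at 30, 0.899 at 29). The plan then randomizes 36 per group (30 × 1.2).

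**How each provision treats a rescue exit between months 3 and 6**

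- Analysis set (9.3): it requires 3-month data only. The patient stays in the set but has no scheduled month-6 value.
- Exclusion (9.4.1): worded for the primary analyses. Whether it extends to month 6 is not stated, and no other default is given.
- Failure-then-success analysis (9.4.1): names only those lost to follow-up, whom Section 7.2 defines as not returning and not contactable. A patient who exits for rescue is known to the site, so the wording does not reach them.
- Carried-forward analysis (9.3): covers terminations, but for EEsAI only. Eosinophil counts, histologic thresholds and EREFS are not covered. Without an early termination visit it may carry forward a good score from before the relapse.
- Early termination visit (6.5.1; 8.4, Visit Months 3, 6 and Early Termination): includes endoscopy with biopsy, EREFS, EEsAI and SDI. After rescue it depends on being safe and feasible. No text assigns its values to month 6.

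**Binary outcomes.** Let N be the patients in the arm, k the rescue exits after month 3, and r the response rate among those remaining.

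- Rate if exits are excluded: r
- Rate if exits count as non-response: r × (N − k)/N
- Overstatement: r × k/N

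Inputs: N = 36 (Section 9.2). The documents do not give k or r. I assume k = 2 to 7 and r = 50% to 70%, with no other missing data. The upper k is 7/36 = 19.4%, close to the plan's 20% dropout allowance, which serves here only as a ceiling for the illustration.

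| Exits of 36 | r = 50% | r = 60% | r = 70% |
|---|---|---|---|
| 0 | 50.0 (gap 0) | 60.0 (gap 0) | 70.0 (gap 0) |
| 2 | 47.2 (gap 2.8) | 56.7 (gap 3.3) | 66.1 (gap 3.9) |
| 4 | 44.4 (gap 5.6) | 53.3 (gap 6.7) | 62.2 (gap 7.8) |
| 6 | 41.7 (gap 8.3) | 50.0 (gap 10.0) | 58.3 (gap 11.7) |
| 7 | 40.3 (gap 9.7) | 48.3 (gap 11.7) | 56.4 (gap 13.6) |

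Entries are the percentage with exits counted as non-response; the gap is in percentage points. Example: 0.60 × 32/36 = 53.3%, so the gap is 6.7.

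**Mean EEsAI decrease.** Assume a true mean decrease of 32 and SD 20. Both come from the Section 9.2 table, which is for 12 weeks; their use at month 6 is an assumption.

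- If exits improve by 20 points less than stayers on average, the bias is f × 20 for exit fraction f: 1.0, 2.0 and 4.0 points at f = 5%, 10% and 20%.
- If exactly the worst fraction f exits, which is the extreme case, the bias is 20 × φ(z_f)/(1 − f), with φ the standard normal density and z_f the f quantile: 2.2, 3.9 and 7.0 points.

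**The case against.** The strongest reply is that the plan nowhere prescribes a completers-only analysis. A reader might infer that month-6 durability is estimated only in patients still in the study. That goes beyond the text: Section 9.4.9 names no population, and the exclusion sentence is limited to primary analyses. This stands. The defect is an unspecified rule, not an explicit wrong one.

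A reader might also infer that every patient whose response fades is removed. That is not so. Patients who relapse without rescue stay and are measured. Section 6.5.1 further says that, where safe and feasible, "use of rescue medications should be delayed until either the 3-month or 6-month assessments are completed", and that after rescue, on the same condition, "the subject should return for an early termination visit". EEsAI is collected at months 4 and 5 and SDI weekly, so many failures would be recorded. These provisions reduce the loss. They do not say how a recorded failure enters the month-6 estimate.

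Dilation at the month-3 endoscopy is not evidence that a response was lost between months 3 and 6. Section 2.1 notes that dysphagia from a stricture can persist after inflammation resolves. Likewise, scoring a rescue exit as histologic failure may override an early termination biopsy that shows response. Both points are fair, and the fix below allows for them.

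Finally, the analysis is listed as exploratory. That limits the consequences, but it is the plan's answer to a stated secondary objective.

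**Conclusion.** The concern holds as a gap in specification with a known direction. Rescue before the month-6 endoscopy forces exit, Section 9.4.9 has no rule that keeps these failures in the estimate, and the only stated default is exclusion. If that default is used, the durability estimate leans upward whenever rescue exits occur.

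The size cannot be determined from the documents. Under the assumptions shown, it is about 3 to 14 percentage points for a response rate and about 1 to 7 EEsAI points for a mean decrease (exit fractions of 5% to 20%). It is zero if nobody exits for rescue.

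A larger figure is tempting. With 20 month-3 responders and 4 rescue exits, 16/16 = 100% against 16/20 = 80% looks like a 20-point overstatement. The documents do not support presenting this as what the plan would report: Section 9.4.9 covers patients randomized to active medication, not month-3 responders, and no exit rate is given. Nor is bias certain, since it depends on exits occurring and on exclusion being applied.

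**What to change.** Add a short rule to Section 9.4.9 for the month-6 outcomes in the 300 mg arm:

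1. For binary outcomes, use all dosed patients as the denominator, with month-3 responders as an additional durability set.
2. Score patients who exit after month 3 for rescue or worsening EoE as non-response at month 6.
3. For the histologic thresholds, add a sensitivity analysis that uses the early termination biopsy when it was taken before rescue.
4. State how early termination values enter the continuous outcomes (EEsAI, peak eosinophil count, EREFS, SDI).
5. Report exits by reason beside the rates, with dilation at the month-3 endoscopy listed separately, and say how exits for other reasons are counted.

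Exit reasons and rescue details are already recorded under Sections 7.1 and 6.5.1, so no new data are needed. The cost is a few sentences, slightly more analysis work and a durability figure that may be less favourable. No change to clinical management is proposed.

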5. Mean change in severity of endoscopic findings as measured by the EoE Endoscopic Reference Score (EREFS) from baseline to 3-months post-treatment.
6. Mean change in the Straumann Dysphagia Instrument (SDI) from baseline to 3-months post-treatment.

Prespecified Exploratory Outcomes

1. Mean change in peripheral blood eosinophil levels from baseline to 3-months post treatment.
2. For patients initially randomized to active medication, the same set of outcomes (as listed above) will be assessed after 6 months of treatment.
3. For patients initially randomized to placebo, a paired analysis will be conducted to compare month 6 to month 3 outcomes.
4. For the same set of outcomes (as listed above), 3-month data for patients initially randomized to active medication (300mg monthly) will be compared to 6 month data for patients initially randomized to placebo and who have completed 3-months of 100mg monthly. This will provide a comparison of the 300mg to the 100mg dose.
5. Adverse events and safety during all time points in the study.

Study Population:	72 adult and adolescent patients with active EoE as measured by both symptomatic and histologic severity.
Phase:	2
Description of Sites/Facilities Enrolling Participants:	4 United States sites. Competitive enrollment.
Description of Study Intervention:	Arm 1: Mepolizumab 300 mg SQ monthly for 6 months. Arm 2: Placebo SQ monthly for 3-months followed by mepolizumab 100mg SQ monthly for 3 months. (Note that both arms are blinded for the entire 6 months)
Study Duration:	3 years
Participant Duration:	10 months

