4 STUDY DESIGN

4.1 OVERALL DESIGN

This is a multi-center, randomized, double blind, parallel-arm, placebo controlled trial of mepolizumab. After the first 3-month blinded phase, there will be a second 3-month blinded phase where all patients receive active medication, but the dose will be lower in the subjects initially randomized to the placebo arm.

In the first arm, subjects will receive mepolizumab 300 mg SQ monthly for 3 months. In the second arm, subjects will receive a placebo SQ injection monthly for 3 months. Both groups will have the injection administered under direct observation in a clinical setting to ensure proper administration and compliance. Each visit will also provide an opportunity for symptom questionnaires to be completed and for blood samples to be drawn. After 3-months (the time point where the primary outcome is assessed), all subjects initially randomized to active treatment will continue with mepolizumab dosing 300 mg SQ monthly and will remain blinded. All subjects initially randomized to placebo will receive mepolizumab 100mg SQ monthly and will remain blinded.

Of note, no dietary changes, dilations, changes in baseline PPI medication dose, changes in inhaled or intranasal steroid doses, or administration or oral, topical/swallowed, or systemic steroids will be allowed during the study period (from consent through the end of treatment period). Subjects will undergo endoscopy after the first blinded phase (at 3 months) and after the second blinded phase (after 6 months).

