4.3 JUSTIFICATION FOR DOSE

The doses have been chosen based on pharmacologic modelling showing that 100-300 mg of mepolizumab, administered SQ on a monthly basis, is sufficient to suppress eosinophil counts in the blood,⁴⁴ and that this often correlates with decreased tissue eosinophilia as well (personal communication, [name]). However, prior studies of EoE used much higher doses (750mg-1500mg;³⁸ 2.5-10mg/kg³⁹), and dose-response of mepolizumab for EoE treatment and histologic response in esophageal tissue is not known. To bridge the existing pharmacologic and clinical data, we have selected the 300mg dose for comparison to placebo for the primary outcome in the first blinded phase of the study, but will also gain response information on the 100 mg dose in the second blinded phase of the study in a planned paired analysis for those initially randomized to placebo.

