9.4.3 ANALYSIS OF THE SECONDARY OUTCOMES(S)

Secondary outcomes are as follows:

- The proportion of patients who have clinical remission as defined by an EEsAI score of ≤ 20 . This will be compared between groups by chi-square.

- The proportion of patient who have a clinical response, as defined by an EEsAI score decrease of ≥ 20 points. This will be compared between groups by chi-square.
- The absolute peak eosinophil count (measured in eos/hpf) after 3-months of treatment. Eosinophil counts will be measured by our previously validated protocol, with central reading of all biopsy samples at the lead site to ensure a consistent reading approach.⁴⁹ This will be compared between groups with a two-sample t-test.
- Levels of histologic response after 3-months of treatment including < 15 , ≤ 6 , and ≤ 1 eos/hpf. This will be compared between groups by chi-square.
- Mean change in severity of endoscopic findings as measured by the EoE Endoscopic Reference Score (EREFS) from baseline to 3-months post-treatment. EREFS is a validated and responsive endoscopic severity score that assesses the five most common endoscopic features of EoE: exudates, rings, edema, furrows, and strictures.^{50, 51} This will be compared between the groups using analysis of covariance.
- Mean change in the Straumann Dysphagia Instrument (SDI) from baseline to 3-months post-treatment. The SDI is a direct measure of dysphagia frequency and severity with a 7-day recall period. The score ranges from 0-9, with higher scores indicating more severe dysphagia. This instrument, while not validated, has been shown to be responsive in at least 2 clinical trials.^{23, 49} This will be compared between the groups using analysis of covariance.

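### Durability at 300 mg (Secondary Objective 2) has no within-patient month 6 versus month 3 contrast, and the 300 mg versus 100 mg comparison is stated without its confounding

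*Combined protocol and SAP*

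**What the plan says.** The Synopsis (1.1) lists as its second secondary objective: "To assess durability of symptomatic and histologic response to mepolizumab after 6 months of treatment in patients initially randomized to the active medication". Its exploratory outcomes add that for this arm "the same set of outcomes (as listed above) will be assessed after 6 months of treatment", with no method. Section 9.4.9 supplies the method: the outcomes "will be assessed after 6 months of treatment. This will be compared between the groups using analysis of covariance".

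Section 4.1 fixes what the other arm receives after month 3: "All subjects initially randomized to placebo will receive mepolizumab 100mg SQ monthly and will remain blinded". For that ex-placebo arm, 9.4.9 states that "a paired analysis will be conducted to compare month 3 to month 6 outcomes", using paired t-tests and McNemar's test. Section 4.3 also refers to the 100 mg information coming "in a planned paired analysis for those initially randomized to placebo". No matching sentence exists for the 300 mg arm.

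For the binary outcomes at month 3, section 9.4.3 says "This will be compared between groups by chi-square".

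The Synopsis and 9.4.9 also set month-3 data from the 300 mg arm against month-6 data from ex-placebo patients who completed three months of 100 mg. They conclude: "This will provide a comparison of the 300mg to the 100mg dose". No test and no limitation are given.

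**The concern.** Durability asks whether a response present at month 3 is still there at month 6 in the same patients. A month-6 comparison with an arm that has just had three months of active drug answers a different question. Its result depends on how well 100 mg works as much as on what the 300 mg arm has kept. The paired analysis that fits the question is assigned to the other arm only, although EEsAI, endoscopy and biopsy are scheduled at months 3 and 6 in both arms (Schedule of Activities, 1.3; visit list for months 3 and 6).

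The sentence on dose raises a separate problem. In that contrast, dose varies together with time in the study, with three earlier months on placebo, and with selection, because patients who need rescue exit as treatment failures (6.5.1) and only completers of 100 mg are used. A reader could draw a dose conclusion that the comparison cannot support.

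**Working it through.** **Plan's own figure.** Section 9.2 gives 30 per group for mean decreases of 15 (placebo) and 32 (mepolizumab), SD 20, α 0.05, power 0.9; 9.4.1 makes tests two-tailed. n = 2(1.960 + 1.282)² × 20² / 17² = 29.1, rounded up to 30. It reproduces. The documents give no sample size or precision figure for the durability or the dose analysis.

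**What the month-6 between-arm difference measures.** The effect is 32 − 15 = 17. Let r be the fraction of it that the 300 mg arm keeps at month 6, and e the 100 mg effect as a fraction of 17. Assume that the 15-point placebo part persists. The difference is (15 + 17r) − (15 + 17e) = 17(r − e).

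| r | e | Change, 300 mg arm | Change, ex-placebo arm | Difference |
|---|---|---|---|---|
| 1 | 1 | 32 | 32 | 0 |
| 0 | 0 | 15 | 15 | 0 |
| 0.5 | 0 | 23.5 | 15 | +8.5 |
| 0.5 | 1 | 23.5 | 32 | −8.5 |

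Full retention and total loss can give the same difference, and the same half loss can give either sign. The separate arm-level changes (32 and 32, or 15 and 15) do tell the first two rows apart.

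**Precision of a paired contrast.** Half-width = t(n−1) × 20√(2(1 − ρ)) / √n, with SD 20 at each month. The month 3 to month 6 correlation ρ is not in the documents and is assumed. n = 24 (30 less 20%) is also an assumption.

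| ρ | n = 30 | n = 24 |
|---|---|---|
| 0.3 | 8.8 | 10.0 |
| 0.5 | 7.5 | 8.4 |
| 0.8 | 4.7 | 5.3 |

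For a half loss of 17/2 = 8.5 points, the paired t-test at n = 30 has power 0.48, 0.61 and 0.94 at these three correlations. The contrast is feasible but only moderately precise.

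**What net change hides.** Assume normality with mean decrease 32 and SD 20 at both months. Then P(Z > (20 − 32)/20) = 0.726, so about 22 of 30 have a decrease of at least 20 points at month 3. With no net change, 0.775 (ρ = 0.3) to 0.883 (ρ = 0.8) of them still respond at month 6. About 5 to 3 patients lose response and as many gain it. Neither arm-level rates nor McNemar's test would show this, but a retention proportion among month-3 responders does. It would be imprecise: 18 of 22 is 82%, Wilson 95% CI 61% to 93%.

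**Method fit.** The month-6 set includes five binary outcomes: EEsAI remission, EEsAI response, and <15, ≤6 and ≤1 eos/hpf. Section 9.4.3 tests these by chi-square at month 3, while 9.4.9 names only ANCOVA at month 6.

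**Dose contrast.** Suppose the doses are truly equivalent, with 30 per arm and SD 20. An assumed month 3 to month 6 shift of 0, 5 or 10 points gives p < 0.05 with probability 0.05, 0.16 or 0.48 (two-sample t-test). The documents give no such shift, so these figures show only how the contrast responds to one.

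**The case against.** The strongest reply is that the objective is already served in part. It asks about response after six months. Assessing the same outcomes at month 6 in the 300 mg arm, with the confidence intervals that 9.4.1 requires for all estimates, gives remission, response and histologic rates at that time, which is one ordinary reading of durability. Section 9.4.9 also plans to follow weekly SDI over the whole study, and 8.2.1 collects it up to month 6. This stands: a reader might infer that Secondary Objective 2 has no analysis at all, and the documents do not support that. What is missing is a named within-patient contrast for EEsAI, histology or EREFS.

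It is also fair that 9.4.9 never says the comparator is the 100 mg arm. That is inferred from the two-arm design, and the undefined comparator is itself part of the defect.

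The correlations and shifts used above are assumed, and at a correlation of 0.3 even the paired interval is wider than an 8.5-point loss. The structure of the dose contrast is visible in its own sentence, the analyses are exploratory, and 9.4.1 reports non-significant tests as inconclusive. These points limit the weight of the concern. They do not supply the missing contrast, and the rule on null results does not restrain a significant but confounded dose finding.

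**Conclusion.** The point holds as one of specification. For a listed secondary objective, the only between-group method named cannot measure retention of the month-3 response and does not fit five of the outcomes it covers. The suitable paired method is given to the other arm only. The dose sentence claims more than a non-randomised comparison across periods can support.

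The result that the between-arm difference can be 0 under opposite durability outcomes rests on the 9.2 planning values and on the placebo part persisting. The paired half-width of 8.8 to 4.7 points at n = 30 rests on SD 20 and assumed correlations of 0.3 to 0.8.

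A reader might go further and conclude that the trial's efficacy result is compromised. It is not: the primary comparison is at month 3 against placebo, and nothing here affects it. The change should be made, but it is not critical to the trial.

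**What to change.** Amend 9.4.9 in three places, and the matching Synopsis text:

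1. For patients randomized to 300 mg who entered the second phase, add a month 6 versus month 3 analysis. For continuous outcomes, give the paired mean difference with 95% CI and a paired t-test. For binary outcomes, give the paired difference in proportions with 95% CI and McNemar's test. Also give the proportion of month-3 responders still in response at month 6, with 95% CI. Count treatment-failure exits as non-response in the binary analyses, and report the number of exits beside the continuous ones. State that there is no concurrent placebo and that non-significance does not show maintained response.
2. Define the groups in the month-6 comparison, describe it as a comparison of two active sequences, and use ANCOVA for continuous and chi-square for binary outcomes.
3. Replace the sentence claiming a dose comparison with a statement that the contrast is non-randomised and descriptive, is confounded with period, prior placebo and selection to month 6, and will be reported as an estimate with 95% CI.

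This needs no new visits or data. The cost is a weaker claim about dose, and a durability estimate that is uncontrolled after month 3 and only moderately precise. Some of the apparent loss of response will be ordinary fluctuation around the threshold.
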